13.3 Pharmacodynamic model of vitamin D3

Time course of inflammatory responses to vitamin D3 treatment will be used to develop the pharmacodynamics model of vitamin D3.

14.0 REGISTRATION GUIDELINE

14.1 Subjects will be registered into the study through submission of the research order form, informed consent, and patient bill of rights to the Clinical Trials Office (CTO) at USC.

15.0 BIOHAZARD COMTAINMENT

Not Applicable

16.0 ETHICAL AND REGULATORY CONSIDERATIONS

All institutional and Federal regulations concerning the Informed Consent form will be fulfilled. The study will be conducted in adherence to ICH Good Clinical Practice.

Appendix I: Study Calendar

Appendix I

	Screening	Day 0	Day 1	Day 7	Day 28	Day 56	Day 70
Informed Consent	X						
Medical History	X						
Medication History	X						
Height, weight	X						
Vital signs ^A	X	X	X	X	X	X	X
Safety labs ^B	X			X			
Pre-screening of 25OHD status	X						
PO drug administration		X					
Blood Pharmacokinetics (PK) ^C		X	X	X	X	X	X
Blood inflammatory biomarkers		X	X	X	X	X	X
Adverse Events		X	X	X	X	X	X

A. Vital signs to include blood pressure, heart rate, temperature, respiratory rate.

B. Safety labs to include comprehensive metabolic panel

C. All subjects will have a pre dose blood PK levels, 2, 4, 6, 8 hours and 1, 7, 28, 56, 70 days post dose of cholecalciferol. A 5mL serum separator tube will be used to collect the blood sample.

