3.0 STUDY DESIGN

This is a pilot study to determine the pharmacokinetics-pharmacodynamics of vitamin D3 in CF patients. Clinically stable CF patients with a history of pancreatic insufficiency (n=6) and matching non-CF subjects (n=6) will be recruited in this study. The presence of pancreatic insufficiency will be based on a known CF genotype associated with pancreatic insufficiency. All subjects will be pre-screened for 25(OH)D status to include those with 25(OH)D levels below 30 ng/mL. The subjects will receive a single oral dose of vitamin D3, known as stoss therapy. The dose of stoss therapy will be based on patient's baseline serum 25-hydroxyvitamin D3 level. For CF patients, the dose will be administered with food and pancreatic enzyme supplement to maintain nutritional status. This dose was chosen because previous studies in pediatric CF patients demonstrated that a large single dose of up to 600,000 IU vitamin D3 raised and maintained sufficient 25(OH)D concentrations over 12 weeks without any signs of adverse events (25, 26).

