8.0 ASSESSMENT OF EFFICACY AND SAFETY

8.1 Side effects/Toxicities to be monitored.

8.11 Possible side effects of vitamin D include: hypercalcemia, nausea, appetite, thirst, frequent urination, constipation, vomiting, abdominal pain, muscle weakness, muscle and joint pain, confusion, lethargy and fatigue (14, 35, 36). To ensure safety of high dose vitamin D in CF patients, we will be assessing the patients' calcium, magnesium, phosphate, albumin and alkaline phosphatases levels, at screening and day 7.

8.12 Long-term toxicities to be monitored after completion of therapy. List side effects/toxicities and define levels.
Long-term vitamin D toxicities have not been determined. Single high intramuscular dose (600,000 IU) of vitamin D3 was shown to be safe in patients with osteoporosis (37), and accidental mega-dose of 2,000,000 IU was well

tolerated, with slightly elevated calcium levels in the first two weeks, in two nursing home patients (38), suggesting that high bolus dose of cholecalciferol is safe.

8.2 Dosage change based on toxicity. Not applicable.

8.3 Adverse Event Reporting: Procedures for reporting unexpected and fatal toxicity should be explained.

8.31 Any significant adverse events that occurs during the course of the study will be documented and reported. The types of event to be reported include Type of event to be reported and timing of reports.

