10.0 CRITERIA FOR EVALUATION AND ENDPOINT DEFINITIONS

Primary Outcome Measure

1. Peak plasma concentrations (C_{max})
2. Time taken to reach the maximum concentration (T_{max})
3. Area under the plasma concentration versus time curve (AUC)

Secondary Outcome Measure

1. Levels of serum inflammatory biomarkers
 - Changes in IL-6, IL-8, TNF- α , IL-1 β , C-reactive protein

11.0 SPECIAL INSTRUCTIONS:

Blood samples will be taken at baseline (0 h) and at 2, 4, 6, 8 hours and 1, 7, 28, 56 and 70 days after intervention. At each defined time points, 5 mL of venous blood will be collected in serum separator tubes (BD Vacutainer) with clot activator (39) to measure serum vitamin D₃ and 25(OH)D₃ concentrations. Samples will be handled with care to minimize sunlight exposure during the time of collection. Samples will be immediately placed on ice and stored in aliquots at -80 °C until analysis. Serum levels of vitamin D₃ and its metabolites will be determined using LC/MS-MS. Levels of inflammatory biomarkers will also be determined at each defined time points.

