13.0 STATISTICAL CONSIDERATIONS

13.1 Pharmacokinetic Analysis

Population pharmacokinetic analysis will be performed using the maximum likelihood estimation via the EM algorithm (MLEM) as implemented in ADAPT 5 (Biomedical Simulations Resource, University of Southern California). Multiple candidate models will be evaluated to identify the model that best describes the observed plasma concentration data for vitamin D3 and 25(OH)D3. The maximum concentration and time to maximum concentration will be determined from the observed data.

Patient demographics, clinical characteristics, and pharmacokinetic parameters will be summarized using descriptive statistics.

Differences in the pharmacokinetic parameters between non-CF controls and CF patients will be determined by non-parametric Wilcoxon-Mann Whitney test.

13.2 Comparison of mean serum and plasma concentrations of inflammatory markers at baseline and 10 weeks post intervention

Mean serum/plasma concentrations of inflammatory biomarkers will be compared between CF and non-CF, as well as within groups. Differences in the mean concentrations of inflammatory markers will be determined by non-parametric Wilcoxon-Mann Whitney test.

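### Each biomarker change rests on one pre-dose value; a second tube at the existing screening draw, with a paired analysis, would cut the variance of the week-10 change by up to 25%

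*Combined protocol and SAP*

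**What the plan says.** - **Biomarker sampling.** Section 11.0 states "Blood samples will be taken at baseline (0 h) and at 2, 4, 6, 8 hours and 1, 7, 28, 56 and 70 days after" dosing, and adds "Levels of inflammatory biomarkers will also be determined at each defined time points". That is one pre-dose sample. In Appendix I the row "Blood inflammatory biomarkers" is marked on Days 0, 1, 7, 28, 56 and 70 and is blank at screening.
- **Blood at screening.** Section 8.11 sets calcium, magnesium, phosphate, albumin and "alkaline phosphatases levels, at screening and day 7". Section 3.0 says "All subjects will be pre-screened for 25(OH)D status to include those with 25(OH)D levels below 30 ng/mL", and the calendar carries a row "Pre-screening of 25OHD status". Informed consent is marked in the same screening column.
- **Endpoint and analysis.** The secondary outcome in section 10.0 is change in the five markers. The heading of section 13.2 is "Comparison of mean serum and plasma concentrations of inflammatory markers at baseline and 10 weeks post intervention". Its text compares CF with non-CF and also compares within groups, and names the Wilcoxon-Mann-Whitney test for these comparisons. Section 13.3 uses the time course for a pharmacodynamic model. No section averages the post-dose visits.
- **Size.** Section 3.0 plans six CF patients and six non-CF subjects, all of whom are dosed. The documents give no effect size, within-subject SD, alpha or power for the biomarkers.

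**The concern.** Every change score subtracts one unreplicated value, so an unusual reading at 0 h passes in full into that patient's change. The secondary objective is the anti-inflammatory effect in adults with CF, which here means six people. With so few, a paired test has no slack: six signed-rank pairs reach two-sided p ≤ 0.05 only if all six changes share a sign (2/64 = 0.031; the next attainable value is 4/64 = 0.0625).

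There is a second loss. Everyone is dosed, so there is no untreated arm, and the plan collects no repeat measurement before dosing. A change at week 10 therefore cannot be set against the ordinary fluctuation of the marker. A screening value would supply the study's only estimate of it, and the chance to collect it ends once the subject is dosed.

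**Working it through.** The plan states no figure for the precision of the biomarker change, so there is none to reproduce.

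**Inputs from the documents.** One pre-dose sample now (b = 1) and two with a screening tube (b = 2). One post-dose sample in the planned contrast, day 70 (k = 1). Six subjects per group.

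**Assumed inputs.** On the log scale, within-subject variance v. Correlation r between the screening and 0 h errors. Variance of the true response between patients, h·v.

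**1. Variance of change.**

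Var(change) = v·[(1 + (b − 1)r)/b + 1/k + h]

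Relative reduction from b = 1 to b = 2: ((1 − r)/2) / (1 + 1/k + h)

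For k = 1:

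| r | h | Variance, b = 1 | Variance, b = 2 | Reduction |
|---|---|---|---|---|
| 0 | 0 | 2.0v | 1.5v | 25.0% |
| 0 | 0.5 | 2.5v | 2.0v | 20.0% |
| 0.3 | 0 | 2.0v | 1.65v | 17.5% |
| 0 | 1 | 3.0v | 2.5v | 16.7% |
| 0.5 | 0 | 2.0v | 1.75v | 12.5% |
| 0.5 | 1 | 3.0v | 2.75v | 8.3% |

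So 25% is the ceiling for the planned contrast. It multiplies the SD of change by √0.75 = 0.866, which is equivalent to 6/0.75 = 8 subjects per group instead of 6. More extreme assumptions give less: r = 0.7 with h = 2 gives 3.7%.

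If the five post-dose days were averaged (k = 5, r = 0, h = 0), 1.2v would become 0.7v, a cut of 41.7%.

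**2. Power of a paired test in six CF patients.** Assume a true 40% fall, δ = −ln(0.6) = 0.511, and reject when all six log changes share a sign. With p = Φ(δ/SD of change), power = p⁶ + (1 − p)⁶.

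| log-SD | Baselines | SD of change | p | Power |
|---|---|---|---|---|
| 0.3 | one | 0.3·√2.0 = 0.424 | 0.886 | 48% |
| 0.3 | two | 0.3·√1.5 = 0.367 | 0.918 | 60% |
| 0.4 | one | 0.4·√2.0 = 0.566 | 0.817 | 30% |
| 0.4 | two | 0.4·√1.5 = 0.490 | 0.851 | 38% |

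These use r = 0 and h = 0. With h = 1, power at log-SD 0.3 goes from 34% to 40% (r = 0) or from 34% to 37% (r = 0.5). At log-SD 0.4 it goes from 21% to 24%, or from 21% to 22%.

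**3. The test as written.** An unpaired comparison of six baseline with six week-10 values keeps the between-subject variance in its noise. Averaging two baselines then lowers the mean variance of the two sets by only 0.25·(1 − ICC): 12.5% at an assumed ICC of 0.5, 5% at 0.8. Simulated power of the Wilcoxon-Mann-Whitney test (same 40% fall, log-SD 0.3, two-sided 0.05) moves from 41% to 47% at ICC 0.5 and from 12% to 13% at ICC 0.8. The paired analysis has to come with the tube.

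**The case against.** The strongest reply is that this is an optional gain on a secondary outcome of a pilot study, that nothing in the documents conflicts, and that the size depends on inputs the documents do not supply. All of that stands, and it is why the point is labelled an improvement. The assumption of one common true response is also doubtful: section 1.0 reports wide variation between individuals in response to vitamin D treatment, though for 25(OH)D outside CF. That is why 25% is given as a ceiling.

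It is also fair that screening may not match Day 0. The documents give no interval between the two, and section 7.4 bars vitamin D3 supplements during the trial without saying whether that period starts before screening. The two values could therefore reflect different supplement states. Recording the interval and supplement use deals with this in interpretation but does not remove it. Tubes would also have to be stored for screened subjects who later prove ineligible, and their number is unknown.

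Four stronger readings are tempting, and the documents do not support them:

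- **A cut of 25–42%.** The upper figure needs five post-dose visits averaged. Section 13.2 compares baseline with week 10 only.
- **The single baseline dominates the error of the change.** With one value before and one after, each contributes half.
- **One noisy baseline can lose the planned result because all six must agree.** That is a property of a paired exact test, not of the unpaired test that section 13.2 names.
- **The pharmacodynamic model inherits the same noise.** Section 13.3 does not say that it works on change from 0 h; a baseline could be estimated from the series, which by section 11.0 also includes the 2–8 h samples.

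**Conclusion.** The point holds as a cheap improvement. For the planned week-10 change analysed within subject, a second baseline lowers the variance by at most 25%, given independent baseline errors and the same true response in every patient. Over the moderate departures tabulated, the range is about 8–20%. The power gain in six CF patients is at most 12 percentage points at log-SD 0.3 and 8 at log-SD 0.4, for an assumed 40% fall. Under the unpaired within-group test now named, little of this is realised. The estimate of untreated variation is a separate benefit that does not depend on these power assumptions, though it does need comparable conditions at screening and Day 0.

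**What to change.** 1. **Appendix I and section 11.0:** add a biomarker sample at screening, as one tube at the existing draw, with the same handling and the same assay batch as the later samples. Record the screening-to-Day-0 interval and any supplement use within it.
2. **Section 13.2, baseline:** define it as the mean of the log screening and log 0 h values. Report the screening-to-0 h difference by group as untreated variation.
3. **Section 13.2, tests:** analyse per-subject log change to week 10, with the signed-rank test within each group and the Wilcoxon-Mann-Whitney test on the changes between CF and non-CF.

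**Cost:** one extra tube per screened subject (those from screen failures can be discarded), 12 more samples assayed for five markers (60 results), and a calendar and consent line. No new visit or venepuncture is needed. Item 3 costs only text and is worth making even if the tube is declined.
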